After validation, the American Society of Gastrointestinal Endoscopy defined guidelines for Preservation and Incorporation of Valuable endoscopic Innovations (PIVI) for real time endoscopic assessment of the histology of diminutive polyps.¹⁴ This guideline defines that a technique should have > 90% agreement for post polypectomy surveillance and a negative predictive value of > 90%. In expert hands, the NICE classification for polyps meets these PIVI criteria, however this could so far not be confirmed outside an expert setting.^{15–17}

We are currently training a deep learning algorithm not only for polyp detection, but also for polyp characterization. Preliminary results show an accuracy of about 70% - 75%. To further optimize this system's performance, additional images and videos are necessary. Therefore, we would like to take the opportunity during the current study to collect images and videos of some of the detected polyps. With the obtained data we would like to further develop the AI tool for characterization of colonic polyps.

3. Aim

The primary aim of the current study is to further prospectively validate a computer-aided detection tool for colorectal polyp detection and evaluate its technical performance and feasibility in daily clinic. In addition, we want to use the obtained data for further development of an AI tool for characterization of colonic polyps.

4. Definitions

Positive detections:

- False positive detection: The AI-tool indicates a structure that is not a polyp (eg. Air bubbles, stools, tools, fold, ...). We further specified three possible types of false positive detections:
 - (1) Clinically irrelevant false positive detections

These are detections that are obviously false and do not need further or close-by inspection by the endoscopists and can be readily recognized by the trained second observer.

We defined this type of false positive detections in 6 subdivisions:

- 1) Stool remnants: hard or soft stools, remnants of pills or vegetables
- 2) Air bubbles
- 3) Anatomical structures: ileocaecal valve, appendix
- 4) Diverticulum: inverted or non-inverted
- 5) Instruments: all possible accessory instruments (e.g. forceps, needle, snare, ...)
- 6) Vascular structures: all vascular structures (venes or arteries), hemorrhoids
- (2) Clinically relevant false positive detections

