These are detections that could not be classified as a an obviously false positive at first sight and which is indicated by the endoscopists as a side that needs further inspection. In case this is not spotted by the endoscopists, the second observer will ask the endoscopists to perform a second or close-by inspection for better evaluation, not showing endoscopic evidence of a polyp

We subdivided this type of false positive detections in 3 subdivisions:

- 1) (Thickened) fold
- 2) Other: mucosal lesions different from normal colonic mucosa
- 3) Not relocated: the detection could not be relocated for additional endoscopic inspection
- (3) Other false positive detections

This is every other false positive detection that does not fit any other class and does not need a second or close-by inspection.

 True positive detection: The AI-tool detects a mucosal lesion that is endoscopically diagnosed to be a polyp at first sight (detected by the endoscopist) or after second and close-by look (if initially missed by the endoscopist).

If in case of doubt the endoscopist takes a biopsy to rule out a polyp, this detection will be considered as a true positive detection by AI.

Negative detections:

- False negative detection: Every polyp that is found by the endoscopist and is not detected by the AI tool before the attempt of endoscopic optical diagnosis. On detection of a polyp, the endoscopist will use a standardized verbal action (ask "Did the system detect the polyp as well?"), to inform the second observer about the detection. Immediately the second observer hits the detection button on the AI system. This is a button that initiates timelimited indicator on the AI coupled screen for 1 second. If no detection is made by the AI system during that time, the endoscopically found polyp is to be considered as a false negative detection for the AI system.

5. Endpoints

Primary endpoint

Total polyp detection during single pass colonoscopy by the artificial intelligence tool in comparison to polyp detection by the endoscopist with endoscopic diagnosis as a gold standard.

Secondary endpoints

- 1. Total polyp detection during single pass colonoscopy by the artificial intelligence tool in comparison to polyp detection by the endoscopist with histological diagnosis as a gold standard.
- 2. The number of extra detected polyps by artificial intelligence with the endoscopic diagnosis as a gold standard.

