- 3. The number of extra detected polyps by artificial intelligence with the histological diagnosis as a gold standard.
- 4. The endoscopist's polyp miss rate defined as the additional detection of polyps during colonoscopy
- 5. The false positive rate during clean withdrawal.

Exploratory endpoints

- 1. Correlation between the Boston Bowel Preparation Score and the number of false positive detections during colonoscopy.
- 2. Correlation between the endoscopist's historical adenoma detection rate and the number of extra detections and false negative detections by the artificial intelligence system.
- 3. Correlation between the polyp size and number of false negatives and additional detections.
- 4. Correlation between the Paris classification and the number of false negatives and additional detections.

- 5. Correlation between the total number of polyps per colonoscopy and additional detections.
- 6. Correlation between the experience of the endoscopist and additional detections.

6. Study Design

This is an investigator-initiated multicentre non-randomized prospective interventional trial to validate the performance of a novel state-of-the-art computer-aided diagnostic (CAD) tool in polyp detection implemented as second observer during routine diagnostic colonoscopy and to evaluate its feasibility in daily endoscopy. Consecutive patients referred for a screening, surveillance or diagnostic colonoscopy will be included. After standard bowel preparation with PEG based solutions, patients will undergo a standard colonoscopy performed by an endoscopist with moderate to high adenoma detection rate (ADR > 20% and < 50%). A second observer, who is not a trained endoscopist, but a person trained for recognition of polyps and endoscopic lesions (see section 8), will follow the procedure on a bedside AI-tool to count the number of detections made by the AI system and categorize the results into positive or negative results as follows (1) true positive, (2) false negative or (3) false positive (detailed description, see section 4).

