Exclusion criteria for study analysis

- Colonic inflammation of > 30cm during colonoscopy
- Incomplete colonoscopy for any reason
- Incomplete recording or technical failure of the artificial intelligence system

8. Study Procedures

Bowel preparation

Before endoscopy patients will be prepared either at home either in hospital with standard bowel preparation according to local practice in the respective research centers, with an oral polyethylene glycol based regimen and if necessary, with an additional water enema. During endoscopy, all residual stools will be removed from the colonic wall by rinsing with water with or without dimeticon. Every subject's bowel preparation will be scored using the Boston Bowel Preparation Scale (BBPS).

Endoscopy, video recording

Endoscopy will be performed in patients on the scheduled appointment as initially made after selection based on referral. Video recording of the procedure will be initiated to record the patient's number upon the case report form before the endoscope is introduced in the anal canal. Before withdrawal, a picture of the caecum needs to be taken. During withdrawal the bowel should be as maximal inflated as possible for a high-quality inspection. A single pass withdrawal will be applied during inspection.

If a polyp is found, it can be resected after an endoscopist's optical assessment. This endoscopist's optical assessment should include description of the polyp size, location, Paris classification and if possible endoscopic diagnosis of most probable histology (hyperplastic, sessile serrated, adenoma or carcinoma).

If more than 5 polyps with apparent hyperplastic morphology are found in the rectosigmoid, the first 5 polyps will be included for analysis of the AI tool performance and will be resected for histological assessment and inclusion in the study. Any additional apparent hyperplastic polyps in the rectosigmoid exceeding the number of 5 will be discarded from the study for practical reasons. Most of these polyps will be hyperplastic and are clinically irrelevant. Additional separate biopsies of these sometimes many polyps will incur unnecessary costs. The entire procedure needs to be recorded as one video.

Second observer

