The second observer will undergo a standardized online training with at least 30-40 endoscopic videos (containing 10 clear videos of false positive detections and > 20-30 videos with difficult detections) for polyp recognition, before the start of the study, to correctly categorize the different detections and to be able to diagnose obvious clinically irrelevant false positive findings by the system.

In the ideal setting, this person has already a medical or endoscopic background (e.g.: endoscopy nurse, medical fellow, endoscopy researcher). Before a person can contribute in this study, this person will have to pass an online examination.

After proper training and passing the examination, this person is present during the entire colonoscopy to record the findings of the AI system. Before starting the procedure, the second observer fills in the patient's and institute characteristics onto the patient's individual case report form (CRF) and starts the bedside AI-system. Once the endoscopist starts, the exact time of insertion is noted on the CRF. During insertion the second observer does not count the AI-detections.

Once the endoscopist reaches the caecum and starts inspection during withdrawal, the second observer notes the time of start at the caecum on the CRF and starts to watch the AI detection system. Every detection made by the AI-system is counted and categorized as described above. When a polyp is resected, the number of the polyp, the number of its container and the description of the endoscopic diagnosis have to be noted on the backside of the CRF. Once endoscopy finishes, the second observer writes down the time of ending.

Histopathological assessment

Histopathological assessment will be done on-site by 2 local histopathologists to assess the type of polyp (hyperplastic, adenoma, sessile serrated or carcinoma in situ) and grade of dysplasia. In case of discrepancy between the two pathologists or between the pathological diagnosis and the endoscopic optical diagnosis a third local pathologist will review the tissue sample to come to a consensus diagnosis. When inconsistencies remain, a central pathologist will review and provide a definite diagnosis.

Baseline assessments

Of every patient entering this study the following characteristics and information will be collected by the principal investigator or one of the sub-investigators.

a. Informed consent

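### When the two pathologists agree, only a mismatch with the endoscopist's optical diagnosis reopens histology, and no blinding of the reviewers is stated

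*Combined protocol and SAP*

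**What the plan says.** Section 8, Histopathological assessment, sets up the reading: "Histopathological assessment will be done on-site by 2 local histopathologists to assess the type of polyp". It then gives two triggers for a third reader. One is a disagreement between the two pathologists. The other is a discrepancy "between the pathological diagnosis and the endoscopic optical diagnosis a third local pathologist will review the tissue sample", with the aim of a consensus. The last step is: "When inconsistencies remain, a central pathologist will review and provide a definite diagnosis". The section does not say whether a mismatch that remains only with the endoscopist counts as an inconsistency. It does not say that any reader is blinded to the optical diagnosis.

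The optical diagnosis comes from Section 8, Endoscopy, video recording. The endoscopist is to record "if possible endoscopic diagnosis of most probable histology (hyperplastic, sessile serrated, adenoma or carcinoma"), so a prediction need not exist for every lesion. The optical list ends in carcinoma and the pathology list in carcinoma in situ. What counts as a discrepancy at that end is not defined.

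Histology is the reference in two secondary endpoints of Section 5. The first compares AI detection "in comparison to polyp detection by the endoscopist with histological diagnosis as a gold standard". The third is "The number of extra detected polyps by artificial intelligence with the histological diagnosis as a gold standard". The primary endpoint and secondary endpoint 2 use the endoscopic diagnosis. On characterization, Section 2 adds: "With the obtained data we would like to further develop the AI tool for characterization of colonic polyps".

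**The concern.** A reference standard should not depend on the call it may be compared with. Here, once the two pathologists agree, the optical diagnosis is the only thing that can reopen their result. An agreed histology error that matches the endoscopist is left alone. An agreed histology result that differs from the endoscopist is reviewed, whether it is right or wrong. The reviewer may know why the sample was sent, because no blinding is stated.

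The direct exposure is polyp type. If final histology labels the lesions used to develop or validate the characterization tool, those labels carry some of the endoscopist's prediction, and agreement between optical diagnosis and histology is raised by the procedure itself. For secondary endpoints 1 and 3 the exposure is narrower: it exists only where the extra read changes whether a resected lesion counts as a polyp at all.

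**Working it through.** **Inputs from the documents.** Two first readers, two triggers, a third reader and a central reader (Section 8); histology as reference for secondary endpoints 1 and 3 (Section 5); the sample size inputs (Section 10).

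**Inputs assumed, because the documents give none.** Error of one histology reading, e: 5% to 15%. Correlation of the first two readers' errors, ρ: 0 to 0.3. Optical accuracy, a: 70% to 90%. Third and central readings have error e and are independent unless stated. Each diagnosis has two categories.

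**1. The plan's own figure.** With accuracies 0.97 and 0.95 and independent calls, the discordant proportion is 0.97×0.05 + 0.95×0.03 = 0.077. The unconditional McNemar formula, two-sided 5% and 90% power, is (1.960√0.077 + 1.282√(0.077 − 0.02²))² / 0.02² ≈ 2019. Exact conditional power at 2084 is 0.8995, so 2084 is reproduced. No histology input enters it.

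**2. Which samples are reopened.**
- Pathologists split: third read, whatever the optical call.
- Pathologists agree and match the optical call: no review, even if both are wrong.
- Pathologists agree and differ from the optical call: third read, even if both are right.
- Pathologists agree and no optical prediction was recorded: no trigger.

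With two categories, review in the third case can only leave the result as it is or move it to the optical call.

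**3. Polyp or not.** Take a true non-polyp that the endoscopist called a polyp, with e = 0.05 and ρ = 0. Both readers wrong: 0.05² = 0.0025. Split: 2×0.05×0.95 = 0.095. Both right: 0.9025.
- Third read on a split only: 0.0025 + 0.095×0.05 = 0.7% labelled polyp.
- Optical trigger added, majority of three decides: an agreeing pair cannot be outvoted, so 0 points are added.
- Optical trigger added, central read decides when the third reader dissents: 0.9025×0.05×0.05 = 0.0023, about 0.2 points, giving 0.95%.
- As the line above, but with third and central errors correlated 0.3: 0.9025×(0.05² + 0.3×0.05×0.95) = 0.0151, about 1.5 points.
- Optical trigger added, every remaining mismatch goes to a deciding central read: 0.9025×0.05 + 0.0025 + 0.095×(0.05 + 0.95×0.05) = 5.7%, about 5.0 points added.

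**4. Polyp type, one worked case.** e = 0.10, ρ = 0, a = 0.80. Both wrong w = 0.01, split s = 0.18, both right r = 0.81.
- Rule S, third read on a split only. Error w + s·e = 0.028, whatever the optical call.
- Rule T, optical trigger, central read only if the third reader dissents from an agreeing pair. Optical call right: w[e + (1−e)e] + s·e = 0.0019 + 0.018 = 0.0199. Optical call wrong: r·e² + w + s·e = 0.0081 + 0.01 + 0.018 = 0.0361.
- Rule U, optical trigger, any remaining mismatch to a deciding central read. Optical call right: w·e + s·e² = 0.0028. Optical call wrong: r·e + w + s[e + (1−e)e] = 0.081 + 0.01 + 0.0342 = 0.1252.

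Total error is a × (error if the call is right) + (1−a) × (error if it is wrong). Agreement with the optical call is a × (1 − error if right) + (1−a) × (error if wrong).

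| Rule | Error if call right | Error if call wrong | Total error | Agreement |
|---|---|---|---|---|
| S | 2.8% | 2.8% | 2.8% | 78.3% |
| T | 2.0% | 3.6% | 2.3% | 79.1% |
| U | 0.3% | 12.5% | 2.7% | 82.3% |

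**5. Over the assumed ranges.** The comparator is the same review given to every sample regardless of the optical call. Against it, agreement with the optical call rises by 0.2 to 2.5 points under rule T and by 1.1 to 8.2 points under rule U. It rose in every scenario.

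**The case against.** The strongest reply is that the extra read makes histology more accurate. Much of that stands. In the worked case total error falls from 2.8% to 2.3% under rule T, and rule T had lower total error than rule S in every scenario run. Under rule U it was sometimes higher: at e = 0.05, ρ = 0 and a = 0.70 it was 1.7% against 0.7%. So a reader who infers that the rule makes the reference less accurate overall goes too far. What is shown is that the remaining error depends on whether the endoscopist was right.

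Other stronger inferences also fail:
- That histology is re-read only on disagreement with the endoscopist. A split between the pathologists is a trigger in its own right.
- That false polyp labels nearly double, 0.05 + 0.95×0.05 = 9.75% against 5%. This needs one first reader and a re-read that decides alone. The plan has two first readers and a central reader.
- That the endoscopist gains over the AI. Lesions found only by the AI are also diagnosed by the endoscopist after the second look, so the rule reaches them too.
- That secondary endpoints 1 and 3 are distorted throughout. They concern detection. A change between adenoma and hyperplastic does not change whether a polyp was detected. The histology list has no category for not a polyp, so how such a result enters these endpoints is undefined. When a biopsy is taken in doubt to rule out a polyp, a negative result is not clearly the discordant one.

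Finally, the documents do not call these endpoints an independent check, nor do they say that histology supplies the labels for the characterization tool. The second is a natural reading, but it is an assumption here.

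**Conclusion.** The point holds in a limited form. Conditional on agreement between the pathologists, the endoscopist's optical diagnosis alone governs whether histology is reopened, without stated blinding, and the final histology can therefore move toward it. The primary endpoint and the 2084 polyps are untouched.

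The size cannot be derived from the documents. For secondary endpoints 1 and 3, assumed independent 5% errors give about 0 to 0.2 points of true non-polyps relabelled as polyps. Correlated third and central errors, or a central read that settles every remaining mismatch, raise that to about 1.5 or 5.0 points in the cases above. The last is one reading of an undefined term, not what the plan states. For polyp type the pull is direct and follows the ranges in step 5. The change is worth making because it is cheap, and because the pre-review diagnosis may not be recoverable unless it is recorded at the time.

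**What to change.** In Section 8:
- State that all study pathologists, including the third and central readers, are blinded to the optical diagnosis and to whether the AI or the endoscopist found the lesion.
- For the analysis, let disagreement between the two pathologists trigger the third read.
- If an optically triggered review is kept, record the pathologists' consensus on the CRF before that review. Use it for secondary endpoints 1 and 3 and for characterization labels, and report the post-review result alongside as a sensitivity analysis.
- Define which inconsistencies go to the central reader, and how a result of no polyp enters the two endpoints.

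The core change costs about a sentence of text and one CRF field; the definitions add a line or two. The statistical cost is real: some genuine pathology errors that the optically triggered review would have corrected stay in the main analysis. That is why both versions should be reported.

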For colorectal polyp detection, several pilot studies introducing automated systems for polyp segmentation and characterisation have recently been published, but they have never been tested in a clinical setting, are limited to one specific endoscopy system, and often biased in terms of image selection (only high quality images), weak ground truth or methodology.^{4–7} There is a definite need to develop a system applicable for different endoscopy systems and that can be validated in a real-life clinical setting.

Due to a very close and successful collaboration with the multidisciplinary Medical Imaging Research Centre in Leuven, an improved artificial intelligence (AI) system was developed in-house and differs from the commercially available systems in the fact that this system is able to incorporate temporal information leading to a significant improvement in polyp segmentation as recently shown in the first pilot study, leading to an accuracy of 97% and only one false positive detection per minute. An illustration of what the AI-tool is able to is shown in figure 1.

Figure 1: Example of current status for real time polyp detection; detected lesions are indicated with a green rectangle

In addition, since the introduction of a colorectal screening program, a steep increase in colonoscopies has occurred leading to a large amount of pathological examinations to differentiate between non-neoplastic (hyperplastic) and neoplastic (adenomas) lesions. This has significant cost implications, taking into account that in about 40-50% of the patients polyps are resected. To accommodate these costs, the NICE classification was developed to enable optical diagnosis of small polyps and to enable a resect and discard strategy what may improve the cost-effectiveness as shown by Hassan *et al.*¹² The latter uses optical diagnosis as a guide to determine the surveillance interval for colonoscopy instead of histology and is potentially cost-saving.¹³

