When a detection is made by the AI system and this detection can clearly be categorized the endoscopist and second observer do not communicate. In case of a detection of the AI-system that was not seen by the endoscopist or is unclear to the second observer, the second observer will ask to re-evaluate the indicated region to determine whether after second look it is a true positive not detected by the endoscopist or a clinically relevant false positive detection of the AI system since it caused the endoscopist to take an extra action. Endoscopists will inspect perform a standard colonoscopy with a single withdrawal, inspecting each segment only once, except when the second observer asks to reinspect a certain area in case of a clinically relevant AI detection. The different timings in each segment will be separately measured with a built-in chronometer in the artificial intelligence tool. Time measurement will be initiated once withdrawal is initiated in the caecum and will be determined for every specific segment. In case of therapeutic actions, time registration will be paused and restarted after completion of this therapeutic act. Automated time calculation is integrated in the AI system and provides an overview of the real withdrawal time and the performed therapeutic time. The entire procedure is recorded. The practical set-up is shown in figure 2.

[figure not shown]

Figure 2: Basic set-up of the computer-aided diagnostic (CAD) tool as second observer during endoscopy. A patient undergoes a diagnostic colonoscopy performed by an experienced endoscopist (ADR > 20% and <50%), while a second observer watches the by the CAD-analyzed video to count and categorize the indicated detections. There is no communication between the endoscopist and the second observer unless a clinically relevant finding is found by the second observer or a polyp or clinically relevant finding is made by the endoscopists.

7. Study Population

Inclusion criteria

- Age ≥40 years
- Referral for screening, surveillance or diagnostic colonoscopy
- Able to give informed consent by the patient or by a legal representative

Exclusion criteria for study inclusion

- <40 years old
- Referral for a therapeutic colonoscopy
- Known Lynch syndrome or FAP syndrome
- Any contraindication for colonoscopy or biopsies of the colon

- Uncontrolled coagulopathy
- Confirmed diagnosis of inflammatory bowel disease prior to the scheduled colonoscopy
- Short bowel or ileostomy
- Pregnancy

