As polyps are clustered within patients, we need to take into account a clustering effect. Based on pilot data the intraclass correlation (ICC) was estimated as 0.003 which can be considered as negligible. (This means that there are no patient-effects, which would mean that probabilities of detection differ between patients).

The sample size calculations below are performed for the number of polyps needed, assuming independence.

- A sample size calculation was performed for a McNemar test for paired proportions.
- Sensitivity is assumed to be >90% (pilot data)
- Power = 90%
- A 5% two-sided significance level a difference in accuracy between AI and endoscopist, assuming respectively 97% and 95% of accuracy
- Indicating a total number of 2084 polyps is needed to prove superiority.

Statistical analyses will be performed according to the accuracy and extra detections. Descriptive statistics will be used for continuous variables and expressed as mean, median and range values. Association BBPS, ADR and location will be examined through logistic regression method, ROC curves, sensitivity and specificity.

11. Informed Consent

Written consent documents will embody the elements of informed consent as described in the Declaration of Helsinki and the ICH Guidelines for GCP and will be in accordance with all applicable laws and regulations. The informed consent form describes the planned and permitted uses, transfers, and disclosures of the subject's personal and personal health information for purposes of conducting the study. The informed consent form further explains the nature of the study, its objectives, and potential risks and benefits, as well as the date informed consent is given. The informed consent form will detail the requirements of the participant and the fact that he or she is free to withdraw at any time without giving a reason and without prejudice to his or her further medical care.

The investigator is responsible for the preparation, content, and IRB or IEC approval of the informed consent form and if applicable, the subject authorization form. The informed consent form must be approved by both the IRB or IEC and the sponsor prior to use.

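### The bowel-preparation endpoint uses a raw false-positive count with no time denominator, and the only analysis sentence naming BBPS lists yes/no-outcome methods without naming an outcome

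*Combined protocol and SAP*

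**What the plan says.** Section 5 (Endpoints), exploratory endpoint 1: "Correlation between the Boston Bowel Preparation Score and the number of false positive detections during colonoscopy". Section 8 (Second observer) shows how the number arises during withdrawal: "Every detection made by the AI-system is counted and categorized as described above". The outcome is therefore 0, 1, 2 and so on per procedure.

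Section 10 (Statistical Consideration) has one sentence on analysing BBPS: "Association BBPS, ADR and location will be examined through logistic regression method, ROC curves, sensitivity and specificity". It gives no outcome, unit of analysis, cut-off, covariate or time adjustment.

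Exposure time is recorded. Section 6 (Study Design) states: "The different timings in each segment will be separately measured with a built-in chronometer in the artificial intelligence tool". It adds: "In case of therapeutic actions, time registration will be paused and restarted after completion of this therapeutic act". Section 8 (Bowel preparation) says that during endoscopy "all residual stools will be removed from the colonic wall by rinsing with water with or without dimeticon"; rinsing is not listed as a reason to pause the clock.

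Secondary endpoint 5 is expressed as a false-positive rate and restricted to clean withdrawal. Neither feature is carried over to exploratory endpoint 1.

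**The concern.** There are two linked gaps.

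1. **Method and outcome do not match.** Logistic regression, ROC curves, sensitivity and specificity need a yes/no outcome. The only endpoint involving BBPS has a count. To use these tools on it, someone must choose a cut-off, and the plan offers none.

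2. **Exposure time is left out.** A procedure watched for longer collects more false positives at the same rate per minute. If withdrawal time differs with preparation quality, the count mixes two things: how the AI behaves in a poorly prepared colon, and how long it was watched.

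A real preparation effect is plausible, since section 4 (Definitions) lists stool remnants and air bubbles among the false-positive types. The trial could nevertheless report that the AI does worse in poorly prepared colons when part or all of the difference is observation time.

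**Working it through.** **Inputs from the protocol.** Pilot performance was "an accuracy of 97% and only one false positive detection per minute" (section 2). Patients: 2084 polyps / 2 per patient = 1042 (section 10). The plan gives no figure of its own for this endpoint, so there is none to reproduce.

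**Step 1: is an any/none split usable?** At 1 per minute the expected count over t minutes is t.
- Poisson: P(at least one) = 1 − exp(−t). At 6 min, 1 − exp(−6) = 99.75%; at 8 min, 1 − exp(−8) = 99.97%. The expected number of patients with none is 1042 × exp(−6) = 2.6 and 1042 × exp(−8) = 0.35.
- Overdispersed, with an assumed gamma variance of 0.25: P(at least one) = 1 − (1 + 0.25t)^(−4). At 6 min, 1 − 2.5^(−4) = 97.4%; at 8 min, 1 − 3^(−4) = 98.8%.

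Either way there is very little variation left to model, and any higher cut-off would have to be invented.

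**Step 2: how the count depends on time.** At a constant 1 per minute, 12 minutes against 8 minutes gives 12/8 = 1.5 times the count with no change in rate.

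**Step 3: how large could the distortion be?** The documents give no link between BBPS and withdrawal time, so the slope (extra minutes per BBPS point lost) is an assumption and is varied. All runs use 1042 patients and no true effect of BBPS on the rate per minute.

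*Set B* (400 trials per setting). Assumed: mean withdrawal 10 min at BBPS 9, SD 2.5, minimum 4; BBPS 3 to 9 with probabilities 0.02, 0.05, 0.10, 0.29, 0.19, 0.15, 0.20. Share of trials with p<0.05:

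| Slope (min/point) | Spearman, raw count, Poisson | Spearman, raw count, gamma variance 0.25 | Logistic on count >10, Poisson | Logistic on count >10, gamma 0.25 | Quasi-Poisson with log(time) offset, Poisson / gamma |
|---|---|---|---|---|---|
| 0 | 4% | 4% | 4% | 5% | 5% / 6% |
| 0.25 | 83% | 48% | 67% | 34% | 4% / 5% |
| 0.5 | 100% | 92% | 99.8% | 80% | 5% / 8% |
| 1.0 | 100% | 100% | 100% | 100% | 4% / 5% |

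Monte Carlo error near 5% is sqrt(0.05 × 0.95 / 400) = 1.1 percentage points.

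*Set A* (300 trials per setting). Assumed: 8 min (SD 2) plus the slope times points below 9, with gamma heterogeneity. Raw-count Spearman rejects in 8%, 52% and 97% at slopes of 0.1, 0.25 and 0.5. A negative binomial model with log-time offset rejects in 5%, 4% and 7%.

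**Step 4: size of the spurious effect.** In set B the mean BBPS is 6.83, so at slope 0.5 the mean time is 10 + 0.5 × (9 − 6.83) = 11.1 min. One point lost multiplies the count by about exp(0.5/11.1) = 1.046, which matches the simulated ratio; with the offset it is 1.00. The effect is small per point, and significance is reached because n is about 1042.

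**The case against.** **A reader might infer that section 10 prescribes logistic regression for this endpoint.** The text does not say so. The sentence groups BBPS with ADR and location and follows a statement about accuracy and extra detections. Location is recorded per polyp, and the ADR endpoint concerns extra detections and false negatives, so a polyp-level yes/no model is a possible reading. Endpoint 1 itself speaks of correlation. What stands is that the endpoint has either an unsuitable method or none. Neither reading uses time: the raw-count correlation and the dichotomised logistic model are both distorted in step 3.

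**A reader might infer that poor preparation does lengthen withdrawal here.** No section says this. Rinsing takes place during endoscopy, which includes insertion, when detections are not counted. The link is plausible only. At zero slope there is no inflation, and at 0.1 min per point there is little.

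**The count may be the intended target.** If the interest is burden per procedure, extra time is part of the preparation effect. That is legitimate, but the plan does not say which is meant, and both can be reported.

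**The any/none result pools all false positives.** Section 4 defines three classes, and a split on clinically relevant ones alone need not be degenerate. This is correct, but the endpoint names no class.

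**The offset is not automatically clean.** The clock pauses for therapy, yet instruments are a counted false-positive type and no section says counting pauses too. Re-inspection prompted by a clinically relevant false positive is not listed as a pause, so time is partly a consequence of the outcome. The first can be settled by defining the counting window; the second is a limitation to state.

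**Conclusion.** The point holds as a gap worth correcting in an exploratory analysis. It is certain from the text that the endpoint is a raw count, that the only analysis sentence naming BBPS lists yes/no-outcome methods without an outcome, and that the recorded withdrawal time is not brought into this endpoint. An any/none split would be nearly uninformative (about 97% to over 99% positive at 6 to 8 minutes, depending on assumed overdispersion).

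The size of the time distortion is conditional. With overdispersion, false rejection for a raw-count correlation is about 8%, 50% and 92-97% at assumed slopes of 0.1, 0.25 and 0.5 min per BBPS point. The upper figures should not be read as a forecast, because slope, BBPS distribution, withdrawal times and dispersion are all assumptions. It also does not follow that withdrawal times go unused throughout the trial: secondary endpoint 5 is a rate and may well use them. The McNemar comparison and its 2084 polyps are untouched.

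**What to change.** In section 10:
- State the outcome for exploratory endpoint 1 as false positives per procedure. Analyse it with a negative binomial (or overdispersed Poisson) model with offset log(withdrawal time) from the chronometer, BBPS as predictor and adjustment for site. Report the rate ratio per BBPS point with its confidence interval.
- Count only detections made while the chronometer runs, so that numerator and offset cover the same period.
- Report the unadjusted count alongside, labelled as per-procedure burden.
- Keep logistic regression and ROC curves for polyp-level yes/no outcomes, and name those outcomes.

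The cost is a few sentences, one additional exploratory model and the work of aligning the counting window with the clock. Times and counts are already collected, and the whole procedure is recorded if the window has to be checked.
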